10.4 Termination of Subjects

10.4.1 Subject Decision

Participation is strictly voluntary, and the research is strictly knowledge driven; therefore, a subject may withdraw from further participation in the study without penalty or harm. Any reason(s) the subject may give for terminating his or her participation will be kept confidential. We will store the study documents according to the procedures outlined in the Confidentiality of Data section of this protocol (Section 9). We will require no further information of the subject and the subject will be compensated for their completed study visits prior to termination.

10.4.2 Investigator Decision

Study personnel (principal investigator, co-investigators, and study coordinator) will be authorized to release a subject from further study participation according to the following guidelines:

- The researcher believes that it is not in the subject's best interest to stay in the study.
- Subject becomes ineligible to participate.
- Subject's condition changes such that she needs treatment that is not allowed while taking part in the study.
- Subject does not follow instructions from the researchers.
- The study is suspended or canceled.

Upon termination of a subject, the investigators will ensure the subject is dismissed with any study documents to which he or she is entitled, as well as guidance for resuming medications safely. Subjects will be compensated for their completed study visits prior to termination. Investigators will require no further obligation or participation from a terminated subject.

11. Protection of human subjects

11.1 Potential benefits of this research

11.1.1 Potential benefits to society

This study will provide new knowledge about the effect of peripheral nerve stimulation on vaginal blood flow for women with intact and damaged spinal cords. These findings may lead to new methods of treating female sexual arousal disorder for women with and without SCI.

11.1.2 Potential benefits to participants

We do not expect participants to benefit directly from this study. It is possible the stimulation session may give participants short-term improvement in sexual function. Others may benefit from the knowledge gained from this study. Researchers may use the knowledge gained in this study to design treatments for sexual dysfunction.

11.2 Risks to Human subjects

Potential risks include release of identifying information, physical discomfort or pain during stimulation, skin irritation from gel and alcohol pad prior to electrode placement, women with SCI could have an increase in blood pressure (autonomic dysreflexia), infection from intravaginal sensors, and women with a history of trauma may feel triggered by the research intervention.

11.2.1 Potential Risks and Protection against risks

See sections 11.2.2 through 11.2.7 for a complete list of potential risks and protections against each risk.

11.2.2 Identifying information

A risk to participating in the study is an increased risk of loss of privacy. Participants personal information will be protected per HIPAA guidelines. Only the study coordinator will keep the necessary PHI (name, address) to recruit and schedule the participant session. Otherwise all references to each participant will be coded. Thus, only one person beyond each participant's normal clinical team (for UMHS patients) will have access to their PHI. If individual subject data is published, then no identifying information will be included. Study files will be maintained in a secure location. Access to computerized data will be restricted to IRB-approved study personnel and will be password protected. Data collection will be limited to the study investigators and study staff. All study personnel who have access to the data will be educated regarding the need to protect confidentiality and the procedures to follow to ensure such protection. The likelihood of this risk is rare.

11.2.3 Electrical stimulation

Electrical stimulation can result in pain at site of stimulation. We will keep stimulation current levels at or below the perception threshold, which is normally below the pain threshold. Subjects will be able to report any discomfort or pain associated with the stimulation and current levels will be decreased until the discomfort is no longer observed. The likelihood of this risk is rare to infrequent.

11.2.4 Skin irritation

Participants skin may be cleaned with a mild abrasive gel and an alcohol pad prior to the placement of electrodes. If this procedure causes discomfort and/or skin irritation, it will be stopped and not performed in the second visit. We anticipate the likelihood of this risk to be rare.

11.2.5 Intravaginal sensor

The intravaginal sensor could cause an infection if it is not properly sterilized or improper sterile technique is used. Vaginal sensors will be properly sterilized between each session and placement of the sensor will be performed by a clinical staff who is trained in sterile procedures such as clean intermittent catheterization. If the sensor shows any signs of damage due to reuse or repeated sterilizations, then it will be replaced. We will have back-up sensors on hand throughout the study. The sensor is specifically designed to be human use only and reused. As sensor placement will be guided by clinical staff who are trained in sterile methods including the

standard clean intermittent (urethra) catheterization procedure, we expect that the likelihood of this risk is rare to infrequent.

11.2.6 History of trauma

Subjects with a history of trauma may feel triggered by the research intervention. To reduce the risk of trauma triggering, patients will be fully informed about the treatment regimen and that their participation is voluntary. If psychological trauma occurs, patients will be referred to our sexual health therapists for treatment. The likelihood of this risk is rare to infrequent.

11.2.7 Spinal cord injured participants

In spinal cord injured participants, electrical stimulation of nerves can lead to autonomic dysreflexia (AD) responses such as increased blood pressure that could have serious consequences to the subject. Risk of autonomic dysreflexia, or syndrome in which there is a sudden onset of excessively high blood pressure is generally limited to patients with injuries at the cervical and upper-thoracic levels. Patients with injuries in levels C4 to T5 have a risk of autonomic dysreflexia, however patients are typically well-educated about it and mitigation for it is well established. These patients have nitroglycerine paste in their regimen already, to mitigate against AD, and we will provide it for any patients who do not have it. During the session, we will have cardiovascular monitors (heart rate, blood pressure) that will be watched for any abnormal increases. The MCRU staff member and clinical research team member(s) present will be aware of these parameters, and will respond as needed by terminating stimulation, helping the subject to relax, applying nitroglycerine paste, and seeking further medical care if needed. Prior to the session we will ask spinal cord injured participants to try to empty their bladder, or if they have done it recently, to help further reduce the likelihood of autonomic dysreflexia. In the at-home daily pelvic diary, spinal cord injury participants will be asked if they have symptoms of AD including headaches, flushing, sweating, or goose bumps (see Section 2.3). The likelihood of this risk is rare (T6-T10 patients) to infrequent (C4-T5 patients).

11.2.8 Reasonableness of risks

The risks of participation in the study are minimal, and if there is pain caused by the stimulation it can be stopped by reducing the stimulation amplitude or stopping stimulation completely. Autonomic dysreflexia risk will be limited based on our subject recruitment, cardiovascular vitals will be tracked, and clinical team members will be prepared to respond if necessary. Psychological discomfort can be reduced with psychological support. Infection can be treated with antibiotics. Study team members are fully trained on protection of human private information, and thus the odds of privacy loss occurring are minimally greater than the participant already faces while getting their normal clinical treatment. The study will provide new human data that has never been addressed before. This presents a significant scientific benefit that may lead to new treatment for a patient population that is significantly underserved.

12. Research Costs

All research-specific costs will be covered by research accounts overseen by the research team. Study participants will not be billed for any research study procedures. Participants will be reimbursed for each study visit and travel expenses.

13. Investigational Drug

There is no involvement of any investigational drug in this study.

14. Investigational Device

There is no involvement of any investigational device in this study.

15. Marketed Drugs/Device

15.1 Device

Transcutaneous electrical nerve stimulator (Empi Select TENS)

15.2 PMA Number

K061650

15.3 Purpose of the device

The Empi TENS unit is used to apply electrical stimulation to the skin, to provide relief for pain through electrodes that accompany the unit. We will use the unit and accompanying electrodes to apply stimulation over cutaneous nerves that may modulate vaginal blood flow - the posterior tibial nerve and the dorsal genital nerve. The selection of stimulation parameters will be similar to normal use of the device for pain.

15.4 Frequency and total duration of use for an individual subject

The TENS device will be used once per subject, for 20 minutes of total stimulation during the test session.

15.5 FDA classification of device

Class 2

15.6 How research use departs from the FDA-approved indication

The Empi SELECT Transcutaneous Electrical Nerve Stimulator Device is used for the symptomatic relief and management of chronic, intractable pain and relief of pain associated with arthritis. It is also used as an adjunctive treatment for post-surgical and post-trauma acute pain. The purpose of using the device in this study is to evaluate whether genital nerve or tibial nerve stimulation will modulate autonomic neural circuits and vaginal blood flow.

15.7 Purpose of evaluation

Our goal is to determine support for a possible new indication for use of the device.

15.8 Risk designation for device

Non-significant risk

15.9 Justify risk level and evaluate safety risk

The device is not an implant. The device does not sustain human life or present a potential for serious health risk. The device does not have a substantial importance in diagnosing, curing, mitigating, or treating disease. The device is used in one short-term skin-surface stimulation sessions. The device applies electrical stimulation through electrodes placed on the skin. It is battery-powered, and thus does not have a ground-fault risk. As noted elsewhere in the protocol, stimulation could lead to pain or discomfort below the electrodes. This is not expected to be significant pain. If observed, stimulation will be reduced or terminated such that the discomfort ceases. Each electrode placement will be performed by study personnel familiar with

proper use of the device.

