2.1 Pre-study surveys

Prior to the first visit, participants will complete five clinically validated surveys:

- 1 The American Urological Association Symptom Index (AUASI) bladder symptom index [19]
- 2 The Female Sexual Function Index (FSFI) [20]
- 3 Fecal Incontinence Severity Index (FISI) [21]
- 4 Patient Assessment of Constipation-Symptoms (PAC-SYM) [22]
- 5 The short-form (SF-36) quality of life survey [23], [24]

Surveys will be completed over the phone or online in REDCap, a standard clinical tool for survey data collection [25]. Each survey is included in section 29.1.

2.2 Study visits 1 & 2

The same steps will be followed for all three Aims. Participants will have two study visits. The interval between visits will be at least one month but not more than five months.

On each study day, subjects will complete a urine pregnancy test. Next, subjects will recline in a comfortable position on an elevated table, with pillows and blankets provided if desired. An MCRU staff member will be available to provide assistance, if needed, in addition to one or more clinical research team members. A vaginal plethysmography transducer (Biopac TSD204) will be inserted about 3 inches into the patient's vagina by a clinical staff member or by the patient with clinician supervision. The transducer measures vaginal pulse amplitude (VPA), the standard clinical technique for assessing genital sexual arousal in women [5], [26]–[28]. No energy is transmitted from the TSD204 to the participant. A heart rate monitor (e.g. electrocardiogram or pulse oximetry) and blood pressure monitor will be placed on the participant's arm, hand, or chest (as is appropriate per monitor) to monitor off-target autonomic responses.

On the first study day, one of the two stimulation approaches will be randomly selected and prepared. For dorsal genital nerve stimulation, two circular 1.25-inch diameter transcutaneous electrical stimulation (TENS)

[figure not shown]

Figure 1. Electrode locations (red dots) for genital nerve stimulation, on either side of the clitoris.

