As shown in Figure 4, during the testing period participants will first view a 5-minute neutral film depicting nature scenes to allow blood flow levels to stabilize. This will be followed by a 10-minute period while the subject watches an erotic film clip for assessment of arousal responses without electrical stimulation. The erotic film clip depicts sexually explicit material of two consenting adults engaging in sexual activities including manual and oral stimulation of breasts and genitals as well as penile-vaginal intercourse depending on the film chosen. A 10-minute clip of the same neutral film will follow, to allow blood flow levels to return to baseline. Five minutes into this film, electrical stimulation will be resumed at the previously determined amplitude. Finally, the subject will view another 10-minute erotic film clip depicting similar sexually explicit material as the first while electrical stimulation remains on as the last sequence in the testing.

At the beginning of the VPA recording sequence, in between each video transition, and at the end of the VPA recording sequence (a total of 5 times), participants will view a 15-30-second screen prompt asking them to record their agreement with the statement, “I feel sexually aroused (e.g. sexually excited, turned on) right now,” according to a 5-point Likert scale: (1) *strongly disagree*, (2) *disagree*, (3) *neutral*, (4) *agree*, and (5) *strongly agree*. At the end of each session participants will be asked their general opinions of that stimulation session, whether it seemed to elicit any genital arousal responses such as lubrication, warmth, tingling, or any

sensations they would characterize as pleasurable, and whether they would consider further use of it.

At the second study day, stimulation using the same steps will be performed at the other location.

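### Section 15.9 supports the non-significant-risk designation with two statements that 11.2.7 and 2.2 contradict, and 10.1 leaves a narrow gap in Medical Monitor review after a first autonomic dysreflexia event

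*Combined protocol and SAP*

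**What the plan says.** **Device risk.** Section 15.8 designates the device non-significant risk. Section 15.9 gives several grounds: it is not an implant, it is battery-powered, it is not of substantial importance in diagnosing or treating disease, and "The device does not sustain human life or present a potential for serious health risk". On exposure, 15.9 says "The device is used in one short-term skin-surface stimulation sessions", and 15.4 agrees: "The TENS device will be used once per subject". The only stimulation harm that 15.9 names is that "stimulation could lead to pain or discomfort below the electrodes", to be handled by lowering or stopping the current.

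**The hazard elsewhere.** Section 11.2 lists autonomic dysreflexia (AD) among the risks. Section 11.2.7 says that in SCI participants "electrical stimulation of nerves can lead to autonomic dysreflexia (AD) responses such as increased blood pressure that could have serious consequences to the subject". It rates the likelihood as rare at T6-T10 and infrequent at C4-T5, and it has heart rate and blood pressure watched during the session. Staff are to "respond as needed by terminating stimulation, helping the subject to relax, applying nitroglycerine paste, and seeking further medical care if needed". Section 11.2.8 refers to AD again.

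**Exposure elsewhere.** Section 2.2 says "Participants will have two study visits" and "At the second study day, stimulation using the same steps will be performed at the other location". Section 3.1 plans 20 women with SCI among 40.

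**Oversight.** Under 10.1 every AE goes promptly to the IRB and the Medical Monitor, and two named team members discuss safety monthly. The Monitor must be consulted when more than one patient has a procedure-related AE, and must review at once if unanticipated AEs form a pattern or an SAE occurs. Section 10.3 lists the SAE criteria and adds a clause under which other important medical events may be classed as SAEs on medical judgment.

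**The concern.** Section 15.9 is where the protocol argues its device-risk level, and an IRB would turn to it for that purpose. On AD it says the opposite of 11.2.7 about the same stimulation in the same study. It refers the reader to other sections for pain but not for AD, and it halves the number of sessions per woman.

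The safeguard 15.9 does offer is to respond to discomfort. Section 3.1 defines AIS A injury as complete, without sensory function, and aims for roughly equal numbers of AIS A and AIS B-C women. Discomfort is a weak signal where sensation is absent. The protection that matters for these women is the cardiovascular monitoring in 11.2.7, which 15.9 does not mention.

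On oversight, what is at stake is the interval between a first treated AD event and the next SCI session, usually in another woman. The Monitor would know of the event. In the situation traced below, nothing obliges the Monitor to consider it before stimulation is applied again.

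**Working it through.** The plan gives no figure to reproduce on this point. The check sets the texts side by side and then counts.

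**Step 1: the two grounds in 15.9.**

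| Topic | 15.9 (and 15.4) | Elsewhere |
|---|---|---|
| Serious harm | None possible from the device | 11.2.7: stimulation can cause AD, with possible serious consequences |
| Stimulation harms weighed | Pain or discomfort at the electrodes | 11.2 and 11.2.7: AD as well |
| Sessions per woman | One | 2.2: two, one per stimulation site |

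The first and third rows are contradictions. The second is an omission.

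**Step 2: exposure.** Inputs are the group sizes in 3.1 and the visits in 2.2.

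- Total planned: 10 + 10 + 20 = 40 women, which agrees with the stated N.
- SCI share: 20/40 = 50%.
- Sessions under 2.2: 40 × 2 = 80 in all, of which 20 × 2 = 40 are in SCI women.
- SCI sessions under the wording of 15.9 and 15.4: 20 × 1 = 20.
- Ratio: 40/20 = 2.

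These are counts of exposure, not of risk. Section 11.2.7 grades AD by injury level, and the split of the 20 women between T6-T10 and higher levels is not given.

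**Step 3: tracing one AD event through 10.1 and 10.3.** Take an event in an SCI woman that is treated in session, without admission or lasting disability.

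1. Notification: yes, promptly, to the IRB and the Monitor.
2. Multiple-patient trigger: fires if another woman has had any procedure-related AE, such as skin irritation or stimulation pain. It does not fire if this woman is the only one affected so far.
3. Unanticipated-pattern trigger: does not fire, since 11.2 lists AD.
4. SAE trigger: fires without discretion on inpatient admission. Otherwise, for this event, it depends on judgment, either that the event was life threatening in the investigator's view or that it counts as an important medical event.
5. Hold on the next session: none stated. Even an SAE brings immediate review of the data but no rule that the next session waits.

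**Step 4: illustration only.** The protocol gives no AD rate. Assume the same per-woman probability p in 20 independent SCI women.

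- P(at least one affected) = 1 − (1 − p)^20
- P(exactly one affected) = 20p(1 − p)^19

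| Assumed p | At least one | Exactly one | Exactly one, given any |
|---|---|---|---|
| 1% | 0.182 | 0.165 | 91% |
| 2% | 0.332 | 0.272 | 82% |
| 5% | 0.642 | 0.377 | 59% |
| 10% | 0.878 | 0.270 | 31% |

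If AD is as uncommon as 11.2.7 suggests, AD events alone would often not fire the multiple-patient trigger. The last column ignores related AEs of other kinds in other women, which would fire it. It is therefore an upper limit on how often that trigger stays silent.

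**The case against.** The strongest reply is that AD is not hidden. It is listed in 11.2, mitigated in 11.2.7 and weighed in 11.2.8, so correcting 15.9 is editorial. The first half of this stands: a reader might infer that the designation is wrong or that the hazard was concealed, and the documents support neither. The other grounds in 15.9 are untouched, and the risk is rated rare to infrequent. But the section that argues the risk level still makes two statements that the protocol contradicts. Disclosure elsewhere does not correct them.

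On oversight, a reader might infer that any AD event short of an SAE escapes the Monitor. That goes too far. Every AE is reported to the Monitor promptly, an admission makes the event an SAE without discretion, and a related AE of any kind in a second woman requires consultation.

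Other safeguards narrow the gap further. A woman's visits are at least one month apart and safety is discussed monthly, so a discussion should normally precede her own second session. Section 10.4.2 lets staff release a woman whose interest is not served by staying, and the diary asks about AD. The names of those who hold the monthly discussion are removed, so it cannot be said whether the Monitor is one of them. None of this covers another SCI woman stimulated within days of a first event.

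It is also fair to say that holding the next session is a proposed standard, not one that the protocol sets and then breaches. For that reason this part is an improvement and not an error.

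**Conclusion.** Two grounds offered for the non-significant-risk designation, the absence of potential for serious harm and the single session, are wrong as written. They concern half the planned sample and understate SCI sessions by a factor of two (20 against 40). The conclusion rests only on the texts and on the planned numbers being recruited. It does not extend to the designation itself, which the documents do not show to be wrong.

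The oversight gap is real but narrow. It applies to an AD event treated in session, without admission or lasting disability, at a time when no other woman has had a related AE. In that case the Monitor's consultation or review depends on the event being judged an SAE. Separately, no rule holds the next SCI session for any event, serious or not. No probability is claimed for such an event, since the rates in the illustration are assumptions.

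Both changes should be made. The first corrects an error, and the second is a cheap safety improvement.

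**What to change.** 1. **Sections 15.9 and 15.4 (correction).** Replace the sentence on serious health risk with text that names AD in SCI women, gives the 11.2.7 likelihood by injury level, and weighs it against the monitoring and responses described there. State two sessions per woman in both sections. Submit the revised text to the IRB for its device-risk determination.

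2. **Section 10.1 (improvement).** Require the existing Medical Monitor to review, before the next SCI session, any AD event in which stimulation was terminated for a rise in blood pressure or AD symptoms, nitroglycerine paste was applied, or further care was sought. Tying the trigger to the action taken avoids needing a blood-pressure threshold, which 11.2.7 does not give.

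The cost is protocol wording and one IRB amendment. The downside is a less favourable stated risk and occasional short delays between SCI sessions. No new committee, visit or measurement is needed.
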